9.3.3 Exclusion Criteria

- 1. Have had previous exposure to ganaxolone.
- 2. Known sensitivity or allergy to any component in the study drug, progesterone, or other related steroid compounds.
- 3. For PCDH19 FPE subjects, have a combination of PCDH19 and SCN1A genetic mutation.
- 4. Exposure to any investigational drug or device \leq 90 days prior to screening, or plans to participate in another drug or device trial at any time during the study.
- Seizures secondary to illicit drug or alcohol use, infection, neoplasm, demyelinating disease, degenerative neurological disease, or central nervous system (CNS) disease deemed progressive, metabolic illness, or progressive degenerative disease.
- 6. Concurrent use of vigabatrin, tiagabine, ezogabine or finasteride is not permitted, nor use of moderate or severe inducers or inhibitors of CYP3A4/5/7. Individuals with prior use of vigabatrin must have had stable visual fields tested twice over the 12 months after the last dose of vigabatrin. A list of CYP3A4/5/7 inhibitors and inducers is included in the Appendix. For Dravet Syndrome subjects the following are also excluded: phenytoin, fosphenytoin, carbamazepine, oxcarbazepine, lamotrigine, rufinamide and stiripentol (Italy specific).
 - Patients on cannabadiol (CBD) products that have shown < 75% improvement must be withdrawn from CBD and be off product >28 days prior to Visit 2.
 - Patients on CBD products that have shown ≥ 75% improvement and have completed or discontinued from the blinded clinical study, are on maintenance CBD for > 6 months or taking epidolex with stable laboratory values and no SAEs will, on a case by case basis, be considered for enrollment. The decision to taper or leave the patient on the drug before adding ganaxolone will be made, if it is believed to be unethical to take the patient off drug and

promote status epilepticus or loss of gained > 75% improvement of seizure control. The patient will need to meet criteria for current entry seizure frequency for ganaxolone study.

- 7. Have any medical condition that, in the investigator's judgment, is considered to be clinically significant and could potentially affect subject safety or study outcome, including but not limited to: clinically significant cardiac, renal, pulmonary, gastrointestinal, hematologic or hepatic conditions; or a condition that affects the absorption, distribution, metabolism or excretion of drugs.
- 8. Have active suicidal plan/intent, or have had active suicidal thoughts in the past 6 months or a suicide attempt in the past 3 years.
- 9. Have Alanine transferase (ALT; SGPT) or Aspartate transferase (AST; SGOT) levels > 3 times upper limits of normal (ULN), or total bilirubin >1.5 time ULN at the baseline visit.
- 10. Are planning to follow a ketogenic diet. If on ketogenic diet for more than 6 months with stable laboratory values and seizure control then enrollment will be made on a case by case basis.
- 11. Is sexually active or pregnant.
- 12. Unwilling to forgo grapefruit and grapefruit juice from diet during the entire clinical trial.

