9.3.2 Inclusion Criteria

- 1. Have parent or legal guardian available and willing to give written informed consent, after being properly informed of the nature and risks of the study and prior to engaging in any study-related procedures.
- 2. Outpatients between 2 and 18 years of age at time of consent.

3. In the opinion of the investigator have confirmed PCDH19 genetic mutation, confirmed CDKL5 genetic mutation or Dravet Syndrome confirmed by a SCN1A mutation, or genetic epilepsy testing confirming a LGS or CSWS condition associated with this genetic phenotype. Refractive cases of LGS or CSWS that remain idiopathic or have prior history of steroid or ACTH response can also be entered if documentation confirms specific genetic defects are not found and prior steroid response clinically occurred.

4. Seizure criteria:

- a. Have uncontrolled cluster seizures (3 or more seizures over the course of 12 hours) every 6 weeks or less during baseline, or bouts of status epilepticus on intermittent basis, or
- b. Have uncontrolled non-clustered seizures (focal dyscognitive, focal convulsive, atypical absences, hemiclonic seizures, spasms, or tonic-spasm seizures) with a frequency ≥4 seizures per 28-day period during baseline, or
- c. Have ≥4 generalized convulsive (tonic-clonic, tonic, clonic, atonic seizures) per 28-day baseline period during baseline, or
- d. Have subclinical CSWS syndrome with or without clinical events on EEG
- 5. Subjects should be on a stable regimen of AED medication, and generally in good health.
- 6. Parent or guardian is able and willing to maintain an accurate and complete daily written seizure calendar for the duration of the study.
- 7. Able and willing to take study medication with food, two or three times daily. Ganaxolone must be administered with food.

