9.5 Efficacy and Safety Variables

9.5.1 Calculation of Baseline

Baseline will be calculated from a maximum of 12 weeks' of seizure calendar data with a minimum of 4 weeks of data required, which should include contiguous retrospective ratings provided after signing informed consent. Acceptable retrospective daily seizure

data include a diary record of the frequency and type of seizures by day. Source data may include a seizure diary or calendar, recorded data from smart phones or other devices. Seizure clusters are to be identified, and the number of seizures in the daily cluster should be counted or given as best estimate.

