9.5.5.2 Visit 2 (Baseline; Week 0)

- Review medical history, background AEDs and other concomitant medications
- Review inclusion/exclusion criteria
- Collect and review seizure calendars
- VAS
- Administer Columbia Suicide Scale assessed for children 7 years and older
- Perform physical and neurological examinations
- Measure vital signs
- Draw blood sample for, hematology, chemistry, trough concomitant AED levels, and allopregnanolone, and related endogenous CNS-active steroids; obtain urine sample from subjects who are toilet trained for urinalysis and pregnancy test for WCBP.
- Dispense study medication and dosing instructions
- Instruct and provide study Subject Seizure Calendar
- EEG

- Screening and Baseline visits may be one visit if the seizure calendar data are sufficient.
- 9.5.5.3 Visit 3 (end of Week 2 + / 3 days)
 - Review background AEDs and other concomitant medications
 - Collect and review seizure calendars; provide new calendars
 - Administer Columbia Suicide Scale assessed for children 7 years and older
 - Perform follow-up physical and neurological examinations
 - Assess for adverse events
 - Measure vital signs
 - Collect bottles from prior visit study medication
 - Adjust dose if necessary
 - Dispense study medication
- 9.5.5.4 Visit 4 (end of Week 4 +/- 3 days)
 - Review background AEDs and other concomitant medications
 - Collect and review seizure calendars; provide new calendars
 - Complete CGII-Clinician Ratings
 - Instruct and collect CGII-Patient/Caregiver Ratings
 - Administer Columbia Suicide Scale assessed for children 7 years and older
 - Perform follow-up physical and neurological examinations
 - Assess for adverse events
 - Measure vital signs
 - 12-lead ECG
 - EEG
 - Collect bottles from prior visit study medication
 - Adjust dose if necessary
 - Dispense study medication
 - Urine Pregnancy Test for WCBP

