6. EFFICACY ANALYSES

All efficacy analyses will be summarized by cohort in the MITT population. These summaries will include only the CDKL5, LGS, and PCDH19 cohorts since only 2 patients were enrolled in the CWS cohort. However, the CWS cohort will be included in the subject data listings. For the analyses of seizures and clusters, the baseline period consists of up to 12 weeks before the first day of treatment, and the 26-week open-label treatment period starts with the day following the first day of treatment until the final visit for subjects who do not enter the OLE and up to the day before the first dose of OLE treatment for those who do. The first day of treatment is not in either period since the times of seizures were not collected.

Seizure diary compliance will be summarized by cohort. The calculated compliance is:
 $100 \times (\text{Number of Days with Available Seizure or Cluster Diary}) / (\text{Last Available Seizure or Cluster Diary Date} - \text{First Available Seizure or Cluster Diary Date} + 1)$.

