6.1 PRIMARY EFFICACY ANALYSIS

The primary efficacy endpoint is the percent change in 28-day total seizure frequency in the 26-week open-label treatment period relative to the baseline in the MITT population. Frequency of total seizures includes all seizure subtypes presented as individual seizures or clusters. Post-baseline 28-day total seizure frequency will be calculated as the total number of individual seizures and clusters in the 26-week open-label treatment period divided by the number of days with available seizure/cluster data in the period, multiplied by 28. Baseline 28-day total seizure

frequency will be calculated as the total number of individual seizures and clusters in the baseline period divided by the number of days with available seizure/cluster count data in the period, multiplied by 28. The calculation for percent change from baseline in 28-day total seizure frequency will be done as follows for each subject:

$$\left(\frac{[(\text{Post-baseline 28-day seizure frequency}) - (\text{Baseline 28-day seizure frequency})]}{(\text{Baseline 28-day seizure frequency})} \right) \times 100\%$$

The baseline and post-baseline values and the arithmetic and percent changes from baseline in 28-day total seizure frequency will be summarized by cohort separately using descriptive statistics in the MITT population and PP population if they differ. A subject data listing will be provided.

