Baseline and post-baseline values and arithmetic changes from baseline in the longest period of time seizure or cluster free will be summarized by cohort separately using descriptive statistics. A subject data listing will be provided.

6.2.9 Proportion of Subjects with >= 25%, 50%, or 75% Reduction in 28-day Total Seizure Frequency (Sum of Individual Seizures and Clusters) Compared with Baseline

An R% responder is an individual whose reduction of percent change from baseline to the end of the 26-week open-label treatment period in 28-day total seizure frequency is greater than or equal to R%. R% will be 25%, 50%, and 75%. Frequency of seizures is based on the sum of the individual seizures and the clusters.

The number and percentage of responders will be summarized by cohort. In addition, for the main 26-week open-label treatment period of the study, a cumulative responder curve figure will be provided, in which the X-axis represents amount of improvement in increments of 5%, and the Y-axis represents the percentage of subjects improving by at least the amount on the X-axis. The cohorts will be presented separately within the figure. A subject data listing will be provided.

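### For a child withdrawn from non-investigational cannabidiol (CBD), the wash-out of just over 28 days covers only the shortest permitted baseline, so up to 55 of 84 baseline days can be on CBD or tapering; a labelled sensitivity analysis is needed.

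*Protocol*

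**What the plan says.** Protocol 9.3.3, exclusion 6, has two CBD bullets. Under the first, a child with less than 75% improvement "must be withdrawn from CBD and be off product >28 days prior to Visit 2". Visit 2 is Week 0, when ganaxolone is dispensed (9.5.5.2). The second bullet covers children with at least 75% improvement, case by case: "The decision to taper or leave the patient on the drug before adding ganaxolone will be made". It states no time off drug for a child who is tapered.

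The baseline window is longer than the wash-out. Protocol 9.5.1 says "Baseline will be calculated from a maximum of 12 weeks", with a 4-week minimum, and lets retrospective diary records count. Protocol 9.5.5.2 adds: "Screening and Baseline visits may be one visit if the seizure calendar data are sufficient". SAP 6 agrees on length: "the baseline period consists of up to 12 weeks before the first day of treatment". SAP 6.1 defines the baseline rate as "the total number of individual seizures and clusters in the baseline period divided by the number of days with available seizure/cluster count data", multiplied by 28. A responder under SAP 6.2.9 is a child whose reduction "in 28-day total seizure frequency is greater than or equal to R"%, for R of 25, 50 and 75, so the same baseline is used there.

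On scope, Protocol Appendix 5 labels the April 2016 version a local amendment for one site. Appendix 6 says the CBD criteria were added for LGS, CSWS and other genetic epilepsies, although the bullet itself names no cohort. SAP 1 follows Amendment 8.1 of August 2017.

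**The concern.** The trial has no control group and about 10 children per cohort, so each child's own baseline is the only comparator. The wash-out matches the shortest baseline but not the longest. A child can comply with every rule and still have a baseline recorded mostly on CBD, followed by treatment days expected to be off it. That child's score then reflects two changes at once. If CBD had been helping, the baseline is too low and ganaxolone's effect is understated. Improvement below 75% also includes no improvement and worsening. If CBD had been worsening seizures, the baseline is too high and the effect is overstated. The direction is therefore not known in advance.

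**Working it through.** **Check on the 12-week baseline.** Protocol 9.1 gives a maximum participation of 94 weeks. 12 (baseline) + 26 + 52 + 4 = 94, so the protocol does allow for a full 12-week baseline.

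**Can a compliant child have CBD days in the baseline?** Yes, by two routes.
- Prospective: families may chart for up to 12 weeks after consent (Protocol 6, SAP 1.3.1). The wash-out is tied to Visit 2, not to screening, so a child can still be on CBD while charting.
- Retrospective: earlier diary records count (Protocol 9.5.1), and screening and baseline may be a single visit.

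**Does another rule close the gap?**
- Inclusion 5 asks for a stable AED regimen but gives no duration and does not name CBD.
- Inclusion 9 requires review of the calendars but does not say which days count.
- Exclusion 4 (90 days before screening) covers 84 days, but only for investigational products. It closes the gap for investigational CBD.
- The per-protocol set (SAP 2.2.3) keeps the child, because no violation occurred.
- SAP 2.1, 6 and 6.1 contain no rule that drops days on CBD.

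**Day count.** More than 28 days is taken as at least 29 whole days off.
- 12 weeks: 84 − 29 = 55 days (65.5%)
- 8 weeks: 56 − 29 = 27 days
- 4 weeks: none

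If the last dose falls on Day −29 instead, the 12-week figure is 56 of 84. The 4-week figure stays at zero.

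**Effect on one child's score.** These inputs are assumptions, because the documents give no CBD effect. The off-CBD rate is 1, CBD lowered it by r on all 55 days, and there was no rebound. Then:
- baseline B = (55(1 − r) + 29)/84
- a true 50% fall scores 0.5/B − 1
- the true fall needed to score 50% is 1 − 0.5B

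| r | B | True 50% fall scores | True fall needed to score 50% |
|---|---|---|---|
| 25% | 70.25/84 = 0.836 | −40.2% | 58.2% |
| 50% | 56.5/84 = 0.673 | −25.7% | 66.4% |
| 74% (edge of the rule) | 43.3/84 = 0.515 | −3.0% | 74.2% |
| −25% (CBD worsened seizures) | 97.75/84 = 1.164 | −57.0% | 41.8% |

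With an 8-week baseline and r = 50%, B = (27 × 0.5 + 29)/56 = 0.759 and the score is −34.1%. If CBD had worsened seizures by 25% and ganaxolone did nothing, the score is 1/1.164 − 1 = −14.1%. In a cohort of 10, one child at r = 50% moves the mean by (50 − 25.7)/10 = 2.4 points.

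**Is a CBD-free baseline simply better?** No. Suppose withdrawal raises the rate by 20% on the 29 off-CBD days and ganaxolone does nothing.
- CBD-free baseline: 1/1.2 − 1 = −16.7%, in ganaxolone's favour.
- Full window at r = 50%: (27.5 + 29 × 1.2)/84 = 0.7417, so 1/0.7417 − 1 = +34.8%.

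The errors run in opposite directions until rebound reaches 27.5/29, or about 95%.

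**Rare clusters.** Inclusion 4a admits a child on this basis: "Have uncontrolled cluster seizures (3 or more seizures over the course of 12 hours) every 6 weeks or less during baseline". At one cluster per 42 days, the chance of none in 29 days is 13/42 = 31% if evenly spaced, or exp(−29/42) = 50% if Poisson. Percent change is then undefined. Using the short window only when it contains an event would bias the score. One cluster in 29 days gives a baseline of 28/29 = 0.97 per 28 days against a true 28/42 = 0.67, so no effect scores as 29/42 − 1 = −31%.

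**The case against.** The strongest reply is that this is a corner case in a descriptive study. The 55 days need a non-investigational CBD user, withdrawal on the last permitted day and a full 12-week calendar. The scores also assume full CBD effect on every earlier day, although some may be taper days, with instant loss of effect and no rebound. The number affected is unknown. There is no hypothesis test, and subject and medication listings (SAP 5 and 6.1) would let a reader find any such child. If CBD was helping, the error is conservative. The CBD wording comes from a local amendment, and the protocol changed afterwards: SAP 11 describes a Protocol 9.5.2 that differs from the one supplied.

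Most of this stands and limits the size of the point. It does not remove the gap. Listings do not change the calculated endpoint or the responder counts, and the conservative direction holds only if CBD was helping.

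A reader might infer more than the documents support:
- **That the cohort results are biased against ganaxolone.** Neither the number of affected children nor the direction is known.
- **That the CBD-free window should replace the primary baseline.** It can be as short as 29 days and may include withdrawal rebound. SAP 11 also shows that PCDH19 has already been analysed and speaks of the other cohorts' analysis in the past tense.
- **That entry to the extension is distorted.** Inclusion 10 can be read as using only the 28-day periods just before entry, so no effect on the 35% rule is claimed.
- **That all CBD users are affected.** Children left on CBD are not, and investigational CBD is covered by exclusion 4.

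**Conclusion.** The point holds in a limited form. Under the supplied protocol, a compliant child withdrawn from non-investigational CBD can have at most 55 of 84 baseline days on CBD or tapering, falling to 27 of 56 and then to none at the 4-week minimum. For that child, the primary endpoint and responder status mix two drug changes. The result is understated if CBD helped and overstated if it worsened seizures. The scores above rest on assumed CBD effects, full effect on all 55 days and no rebound.

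Under the second bullet the overlap could be larger, because no time off drug is stated. On the purpose given in Appendix 6, LGS is the main summarised cohort exposed, since SAP 6 leaves CSWS out of the summaries. Whether the same CBD wording applied under Amendment 8.1 cannot be told from these documents. The SAP's own 12-week baseline has no CBD rule. This warrants a sensitivity analysis, not a new primary baseline.

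**What to change.** Keep the full-window baseline as the primary analysis. Add to SAP 6.1 and 6.2.9 a labelled sensitivity analysis with these rules:
- For any child who stopped CBD within 84 days before first dose, count only baseline days after the last CBD dose.
- Flag these children in the listings and state how many there are. If there are none, one sentence is enough.
- Where the CBD-free window has no events or is under 28 days, report percent change as not calculable in the sensitivity analysis and list the child. Do not choose the window by whether it contains an event.
- Where the CBD stop date is partial, use the latest possible date and flag it. This matches the direction of the stop-date imputation in SAP 5.
- Show both results together and state the downside: the CBD-free baseline can be as short as 29 days and may include rebound, which favours ganaxolone.

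The cost is one SAP rule and one extra table, using medication stop dates already collected. For any future enrolment, the protocol should count only days after the last CBD dose in the baseline, including for children tapered under the second bullet. With the 4-week minimum, that means at least 28 days off drug. This protocol edit cannot help children already enrolled.

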9.3.4 Removal of Subjects from the Study

9.3.4.1 Investigator-initiated withdrawal of a subject

All subjects have the right to withdraw from the clinical study at any time, as stated in the informed consent form (ICF). The Investigator may discontinue subjects from the clinical study if the subject's condition changes such that the Investigator feels it is not in her best interest to continue, or if she develops a concomitant illness that necessitates treatment which might affect the outcome of the investigation, or if the subject is non-compliant.

Discontinuation decisions will be made at each participating site by the Investigator. If feasible, the process of discontinuation should be discussed with the Study Principal Investigator and the Sponsor.

9.3.4.2 Early Termination Procedures

Subjects who are terminated from the study will be asked to return to the study center for a final safety assessment, initiate a down-titration, and to return unused study medication and to deliver remaining seizure calendars.

9.3.4.3 Consequences of Early Termination

The protocol suggests dose de-escalation of study medication over one to four weeks depending upon dose and duration of treatment. This recommendation is based on cumulative evidence from various classes of CNS drugs that slow taper is beneficial. It is possible that abrupt cessation of the drug might cause discontinuation symptoms. Every effort will be made to ensure implementation of the down-titration.

9.4 Treatments

9.4.1 Treatments administered

Study medication will be provided as either oral suspension or capsules. Ganaxolone oral suspension should be administered through an oral dosing syringe three times daily (TID) by a parent or guardian, following the morning, midday, and evening meal or snack. Each dose should be separated by a minimum of 4 hours and a maximum of 8 hours. A missed dose of ganaxolone suspension may be taken up to 4 hours before the next scheduled dose, otherwise, the missed dose should not be given.

Ganaxolone capsules will be administered two times daily (BID), following the morning and evening meal or snack. A missed dose of ganaxolone capsules may be taken up to 8 hours before the next scheduled dose, otherwise, the missed dose should not be given.

9.4.2 Identity of Investigational Products

Ganaxolone (3α-hydroxy-3β-methyl-5α-pregnan-20-one) suspension contains ganaxolone (50 mg ganaxolone/mL), hydroxypropyl methylcellulose, polyvinyl alcohol, sodium lauryl sulfate, simethicone, methyl paraben, propyl paraben, sodium benzoate, citric acid, and sodium citrate at pH 3.8 – 4.2 and is sweetened with sucralose and flavored with artificial cherry. The suspension has a milky appearance and is packaged in HDPE bottles with a child resistant closure. Ganaxolone will be supplied at a concentration of 50 mg/mL (ganaxolone equivalent) in 120 mL bottles, containing 110 mL ganaxolone.

Ganaxolone capsules will be provided in size 00 white/opaque gelatin capsules packaged in HDPE bottles with a foil induction seal and child resistant closure. Each capsule contains either 200 mg or 225mg ganaxolone (3α-hydroxy-3β-methyl-5α-pregnan-20-one), and hydroxypropyl methylcellulose, sucrose, polyethylene glycol 3350, polyethylene glycol 400, sodium lauryl sulfate, sodium benzoate, citric acid anhydrous, sodium methyl paraben, microcrystalline cellulose, 30% Simethicone Emulsion, gelatin capsules, polysorbate 80, and sodium chloride.

All study medication will be stored at the research pharmacy prior to dispensing, or in a locked cabinet accessible only to members of the investigative research team after the completion of each study visit. Study medication (oral suspension and capsules) should be stored at room temperature 15°C to 25°C (59°F to 86°F).

